5.5 Schedule of study assessments

Table 2: Schedule of study assessments

	Baseline	1 week after Intervention completed/1 week after doctor's appointment	3 months after intervention completed	Lost to Follow-Up/Dropouts
Demographics	X			
Medications and comorbidities	X			
Surveys				
RAPID3	X	X	X	
Social Support Survey	X	X	X	
Patient Activation Measure (PAM)	X	X	X	
Patient Health Questionnaire – 8 (PHQ- 8)	X	X	X	

Medication Understanding and Use Self-Efficacy Scale (MUSE)	X	X	X	
The General Self-Efficacy Scale (GSF)	X	X	X	
Outcomes				
Cholesterol test		X	X	
Initiating lipid lowering therapy		X	X	
Program Evaluation				
Evaluation Survey		X		X
Focus Group/Interview		X		X

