2. INTRODUCTION

CVD is the most common cause of death among patients with RA. Several studies showed a 50-60% increased risk of death from myocardial infarction and stroke in patients with RA compared with the general population, with the standardized mortality ratio attributable to CVD ranging from 1.13-5.15.¹⁻⁶ Aggressive treatment of RA decreases CVD morbidity and mortality, but there is evidence that many patients do not benefit from the “treat to target” paradigm and do not in fact receive sufficiently aggressive RA treatment. Thus, CVD risk assessment through cholesterol testing among patients with RA remains an important CVD risk reduction strategy.⁷⁻¹¹

Several studies have reported that the prevalence of hyperlipidemia in patients with RA is lower than in those without RA. However, the relationship between lipids, RA, and CVD risk is complicated by RA therapies that have been associated with increased lipid levels.^{12,13} We have reported previously that three different combination therapies were associated with increased lipid levels after 6 months of treatment.¹² Nevertheless, the American Heart Association/American College of Cardiology recommend following their guidelines applicable to the general population for CVD risk assessment, including cholesterol testing.

Although primary care physicians (PCPs) test RA patients’ lipids more frequently than rheumatologists, overall testing remains suboptimal, with only 44% or fewer patients with RA tested, compared with 79% of patients with diabetes mellitus (DM), another CVD risk factor that is more widely appreciated by PCPs. A significant knowledge gap has been reported among PCPs regarding RA as a CVD risk factor, with 68% of PCPs frequently failing to identify RA as a CVD risk factor,¹⁴ suggesting that specific interventions for these patients may be warranted.

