5. STUDY POPULATION

5.1 Study population

Inclusion Criteria

- Have RA
- Age between 40 and 75 years (inclusive)

- Provide a date of their next appointment with their rheumatologist or other physician on their care team
- Willing to work with a peer coach
- Speaks English
- Have a phone
- Has access to the internet
- Resides or lives in the US

Exclusion criteria

- Do not have RA
- Younger than age 40 or older than age 75
- Taking a statin
- Known history of diabetes.
- Known history of CVD defined by:
 - Open heart surgery
 - Coronary angioplasty
 - History of heart failure
 - History of heart attack or stroke

Participants will be screened using a REDCap screening survey. If participants answer yes to any of the exclusion criteria questions, the survey skips to the end, and participants will be informed that they are not eligible. The age range for the inclusion criteria reflects the age range of the current AHA guidelines for risk assessment for CVD. The exclusion of established CVD reflects differences in national guidelines on the management of patients with established CVD vs. preventing CVD. The overall goal of this research is to discover effective strategies to prevent CVD, therefore we focus here on primary prevention.

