7.3 Baseline telephone call (All subjects in the study)

The blinded research assistant will perform this call. Assessments at this phone call will include:

- Verify that subjects have completed the baseline data collection forms sent via email through REDCap:
 - Demographic data including gender, and race and ethnicity
 - RA history
 - General medical history
 - Surgical history
 - Surveys
 - RAPID3
 - Social Support Survey
 - Patient Activation Measure (PAM)
 - Patient Health Questionnaire – 8 (PHQ- 8)
 - The General Self-Efficacy Scale (GSF)
 - Medication Understanding and Use Self-Efficacy Scale (MUSE)

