8. ANALYSIS AND STATISTICS

8.1 Power Calculations and Sample Size

The primary outcome measure is the percentage of patients in each arm that had a lipid panel checked or initiated LLT. Assuming 80% of the subjects in the intervention group have their lipids checked within the 3 months of the study, and 60% of the subjects in the control group have their lipid checked N=64 subjects per group would have at least 80% power to detect a margin difference of 20%, for a one-sided test and significance level of 0.05. We recognize that the sample of 128 subjects is modest, which reflects the pilot nature of the study in the context of a training grant. We will use data from this pilot study to design a more definitive trial powered to detect smaller differences in the primary outcome, and to compare usual care with the intervention.

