8.2 Data Analysis

To analyze the data, descriptive analyses (means, medians, standard deviations, proportions, and frequency distributions) and correlation analyses (Spearman/Pearson rank correlations) will be conducted to assess and describe the cohort. Baseline comparability between study arms will be assessed with parametric and nonparametric analyses including two sample t-tests, Wilcoxon Rank Sum, and Chi-Square tests of proportions. Every effort will be made to keep subjects in the study for the entire follow-up. Analysis will be based on intention-to-treat, regardless of whether the subject completed the intervention program. The primary outcome is the percentage of patients with lipids checked (available now through national laboratory chain) or that reported having their lipids checked. Secondary outcomes include the percentage of subjects that reported initiating LLT, self-efficacy, and patient activation as described above. We will determine these outcomes in each group (self-administered online learning program and the CARE RA arm) as well as differences in these outcomes between the groups. Two-sided t-tests will be used to calculate differences and P values ≤ 0.05 will be considered statistically significant. We will examine differences in socio-demographics, disease severity, and depressive symptoms. These characteristics will be included in a multivariable logistic regression model to determine their association with the outcome (lipids being checked) and potentially increase the statistical power of the test of group differences.

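### The primary outcome is defined with conflicting windows and no prior cholesterol test is recorded, so tests done before randomisation can count as successes and no way to separate them is specified

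*Combined protocol and SAP*

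**What the plan says.** One entry criterion in 5.1 reads "Provide a date of their next appointment with their rheumatologist or other physician on their care team". The exclusions cover statin use, diabetes and established CVD. No criterion concerns a recent lipid test.

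Table 2 (5.5) has the row "Cholesterol test X X", with both marks under post-baseline columns. Section 7.3 gives the task of the baseline call as "Verify that subjects have completed the baseline data collection forms sent via email through REDCap". It lists demographics, RA, medical and surgical history, and six surveys. No prior lipid test or test date is named. By contrast, 4.2 asks prospective peer coaches whether they were tested in the previous two years.

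The primary outcome appears in several forms:

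| Place | What counts | Window |
|---|---|---|
| Summary | CVD risk assessment by the physician | Upcoming appointment at the end of the intervention; looked at again three months later |
| 3.1 | Risk assessment, or hearing from the provider that one was already done | One-year look-back for the second route |
| 8.1 | Lipid panel, or LLT started | "Assuming 80% of the subjects in the intervention group have their lipids checked within the 3 months of the study" |
| 8.2 | "The primary outcome is the percentage of patients with lipids checked (available now through national laboratory chain) or that reported having their lipids checked" | None; LLT initiation is a secondary outcome here |
| Table 4 (section 9) | Cholesterol test | During the programme, by one week after, by three months after |

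The logistic model in 8.2 uses socio-demographic factors, depressive symptoms and disease severity. Section 5.4 describes a computer-generated allocation list and mentions no stratification.

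**The concern.** Take a subject tested two months before enrolment and not retested. Read alone, 8.2 lets a laboratory record or a self-report of that test make the subject a success. Under 3.1 the subject is a success only if the provider mentions the test. Under 8.1 the subject is a failure unless LLT is started. The plan does not say which reading governs, and no named baseline item identifies such subjects.

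Two things are at stake. If prior tests count equally in both arms, they add successes that neither arm produced and shrink the difference. If they count only once discovered, the arms may differ in discovery: Session 4 of CARE RA rehearses asking for a test, while controls get the same online modules to view alone. A difference in the composite would then not have to mean that more people were tested. The pilot's rates are also meant to inform the definitive trial, so the ambiguity would carry forward.

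**Working it through.** **Inputs.** From 8.1: 80% versus 60%, n = 64 per arm, at least 80% power, "for a one-sided test and significance level of 0.05". From the Introduction: "overall testing remains suboptimal, with only 44% or fewer patients with RA tested", with no period stated. The share q of enrolled subjects with a prior test that counts is not given, so it is an assumed range. 44% is included only because it is the one background figure available.

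**1. The plan's own figure.** With pooled variance under the null and no continuity correction,

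power = Φ{[d − 1.645·√(2p̄(1−p̄)/n)] / √([p₁(1−p₁) + p₀(1−p₀)]/n)}.

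Here d = 0.20 and p̄ = 0.70. The null standard error is √(2 × 0.70 × 0.30/64) = 0.0810 and the alternative one is √((0.16 + 0.24)/64) = 0.0791. So (0.20 − 1.645 × 0.0810)/0.0791 = 0.844, and the power is 0.80. The plan's 64 per arm reproduces.

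**2. Illustration A: 60% and 80% describe new testing, and every prior test counts in both arms.** Rates are q + (1−q) × 0.60 and q + (1−q) × 0.80, so the difference is (1−q) × 20 points.

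| q (assumed) | Control vs CARE RA | Difference (points) | One-sided power, 64 per arm | n per arm for 80% (one-sided) |
|---|---|---|---|---|
| 0% | 60% vs 80% | 20 | 0.80 | 64 |
| 10% | 64% vs 82% | 18 | 0.75 | 75 |
| 20% | 68% vs 84% | 16 | 0.69 | 88 |
| 30% | 72% vs 86% | 14 | 0.62 | 104 |
| 44% | 77.6% vs 88.8% | 11.2 | 0.52 | 137 |

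**3. Illustration B: 60% and 80% already include prior tests.** The overall rates do not change, so power stays at about 0.80. The implied new-test rates are (0.60−q)/(1−q) and (0.80−q)/(1−q): 50% vs 75% at q = 20%, and 29% vs 64% at q = 44%.

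**4. Chance imbalance.** The standard deviation of the between-arm difference in q is √(2q(1−q)/64): 7 points at q = 20% and 9 points at q = 44%. This is ordinary sampling error, but part of it could be removed if prior testing were recorded before randomisation.

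**5. Differential discovery under 3.1.** Assume q = 44%, new testing at 60% in both arms among those not already tested, and old tests discovered by 80% (CARE RA) versus 60% (control). The rates are 0.44 × 0.80 + 0.56 × 0.60 = 68.8% and 0.44 × 0.60 + 0.56 × 0.60 = 60.0%. The composite differs by 8.8 points with no difference in new testing. At q = 20% the same inputs give 64% vs 60%. The discovery rates are assumptions; the documents give none.

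A separate matter is that 8.2 states "Two-sided t-tests will be used to calculate differences and P values ≤ 0.05 will be considered statistically significant". At two-sided 0.05, 64 per arm gives power 0.70 even with q = 0.

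**The case against.** A reader might infer that the outcome has no start date anywhere. That is true only of 8.2. The summary, 8.1 and Table 4 all tie the outcome to the study period, and 3.1 sets a one-year look-back. The defect is that these windows conflict. The blank baseline cell in Table 2 is also normal for an outcome row; what matters is that no other baseline item fills the gap.

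The composite in 3.1 is a declared choice. Under it the success is learning from the provider, which happens after randomisation and is what the programme trains people to prompt. On that reading, discovered tests are part of the intended effect and not contamination. This stands, and it is why the composite may be kept. It does not settle which definition is analysed, and it does not let a reader of the result tell new tests from discovered ones.

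A reader might also infer that prior tests cannot be adjusted for. The documents do not go that far. Laboratory-chain data in 8.2 might date some tests, and the general medical history in 7.3 might capture others. Neither use is specified.

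Finally, randomisation balances prior testing in expectation. Leaving it out of the model does not by itself bias the comparison, and the study calls itself a pilot. Both points stand and limit the severity.

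**Conclusion.** The point holds as a conflict of definitions combined with a missing baseline item. A test done before randomisation can count under 3.1 or 8.2 but not under 8.1, and the plan specifies no means of separating such tests or adjusting for them. The consequences are dilution if prior tests count in both arms, lost precision, chance imbalance, and a composite difference that may partly reflect discovery of old tests.

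The size cannot be established. The loss of power to 0.75, 0.69 or 0.52 needs both an assumed q (10%, 20%, 44%) and the reading of 60% and 80% as new testing only; on the other reading there is no loss. The 44% describes RA patients in general, whereas this trial excludes statin users, diabetes and CVD, so its transfer is unknown. A reader might infer that the trial is underpowered for this reason, or that its result will favour CARE RA. The documents support neither, because dilution and differential discovery push in opposite directions and nothing shows which would dominate.

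Should-fix: it decides what the primary result means, and the remedy is cheap.

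**What to change.** - Use one outcome definition and one window in the summary, 3.1, 8.1 and 8.2, and say whether starting LLT is part of it. State whether 60% and 80% refer to new tests or to the composite.
- Ask the date of the last cholesterol test at screening. It should not wait for the baseline form, because 5.4 has subjects randomised and told their arm before they complete that form. Section 5.4 describes more than one screening route, so the item belongs on each.
- Record the test date at both outcome calls.
- Report new post-randomisation tests and discovered past-year tests as separate components. The 3.1 composite may be kept alongside them.
- Add prior-year test (yes/no/unknown) as a prespecified covariate in the logistic model already planned in 8.2.

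The cost is one screening question, one date field at each outcome call, one covariate and an edit to four sections. Self-reported dates will be imprecise. The new-test rate may look lower, because recently tested subjects who are not retested count as failures on that component.

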6. STUDY TREATMENTS

6.1 CARE RA arm

- Subjects in the CARE RA arm will have a Zoom call with the unblinded research assistant to review the study procedures relevant to the study arm one week before their Session 1 call with the peer coach. The subject will have an opportunity to ask any questions that they might have before initiating the program.
- The unblinded research assistant will remind the subject about the call with their assigned peer coach for Session 1.
- The unblinded research assistant will call the subject twice over the 5-week intervention period to check on them and to remind the subject of the second data collection point one week after the intervention has ended. These calls will also serve as intervention fidelity checks to assure that the sessions are occurring as scheduled and that the peer coach is interacting with the subject in a manner concordant with training. We will also remind subjects that they can call the study telephone number or contact the research team by email with questions.

6.2 Self-administered online learning arm

- Subjects will receive the same tutorial on the PALS by an unblinded research assistant (via phone/Zoom) on how to access and navigate the PALS (e.g. searching for articles, viewing the evidence summary, watching the videos, completing the self-assessment question after each PALS module).
- They will receive the list of PALS RKOs that correspond to the CARE RA curriculum by email. The mailing will include reminders of how to access the PALS and find the CARE RA PALS RKOs.
- The unblinded research assistant will call the subject twice over the next 5 weeks to remind them that they are in the study, give an opportunity to ask any questions, and remind them of the upcoming assessment points. The research assistant will avoid discussing the PALS unless the subject has specific questions to assure that these retention calls are not interventions.

7. STUDY PROCEDURES AND SCHEDULE

7.1 Intervention fidelity measures

A careful assessment of intervention implementation can provide insights into which aspects of the intervention were particularly effective. We will use several strategies to monitor intervention fidelity.

First, we will ask peer coaches to use Zoom teleconference calls for intervention delivery and record the weekly sessions between peer coaches and subjects. The goal of these recordings is to monitor fidelity of the intervention and monitor duration of the calls. These secure calls will be recorded and stored in the secure and HIPAA compliant server of the WCM Division of GIM. Study staff will review each session and use a checklist to assess intervention fidelity for each session.

Second, the peer coaches will have a checklist that they will have to complete as they go through the call of all the activities and topics that they have to cover in each session, which will ensure that these are completed by the end of each call. We will collect these checklists and compare the self-assessment of the coach to those of the study team based on their review of the Zoom call recordings. In the future larger trial, we will use these comparisons to plan for how to monitor intervention fidelity.

Third, we will monitor intervention implementation on an ongoing basis through weekly teleconferences with peer coaches, and weekly outreach to each peer coach individually throughout the intervention period. We will provide updates on the progress of the study, collaboratively troubleshoot problems, and provide ongoing advice, which often stems from other peers. At these calls, coaches will be asked to report on their clients and progress, giving the opportunity to reinforce the study protocol and MI skills.

Fourth, the research team will contact each subject twice over the 5-week intervention period to check on how the intervention is unfolding from the subject perspective.

7.2 Data collection:

All subjects will receive a baseline telephone call, the post-intervention follow up call, and the 3-month/final follow up call from the study team (Table 2). Subjects who are lost to follow-up or drop out of the study before completion will be contacted to complete the program evaluation portions of the intervention.

We will use REDCap to collect the data at baseline, post-intervention, and final follow up. The subject will receive a REDCap link via email that they will click to access the surveys at each data collection point. A blinded research assistant from WCM will follow up by phone with those subjects that have not completed or partially completed the surveys to minimize missing data.

Session	Objectives	Activity/Assignment	PALS - Renewable Knowledge Objects (RKOs)
1. "Introduction to the CARE RA Program"	
 1. Get to know each other 2. Introduce the CArteriovascular Risk assEssment Program for Rheumatoid Arthritis (CARE RA) program 3. Introduce the client to the Patient Activated Learning System (PALS) 	
 A. Verify contact information and receipt of Activity Book B. Get to know each other C. Introduce the CARE RA program D. Introduce the PALS E. Rules and Responsibilities F. Sign contract G. PALS assignments (RKOs) for Session 2 H. Schedule Session 2 call 	None for Session 1
2. "RA and My Heart"	
 1. Learn how RA affects your heart 2. Learn why a cholesterol test is needed to assess risk for heart attack and stroke 	
 A. Greetings between coaches and clients B. Verify the client has reviewed the RKOs and introduction to Session 2 C. Review of PALS assignments for Session 2 D. CARE RA Highlights of Session 2 E. Plans for Session 3 F. PALS assignments for Session 3 G. Schedule Session 3 call 	
Required:
 
 - How can rheumatoid arthritis (RA) affect my body and my health? - What does atherosclerotic cardiovascular disease (ASCVD) risk mean? - How does rheumatoid arthritis (RA) affect my heart? - How can I lower my risk of heart disease if I have rheumatoid arthritis (RA)? - What is cholesterol? - Do I need a cholesterol test if I have rheumatoid arthritis (RA)? 
Learn more:
 
 - What is rheumatoid arthritis (RA)? - How is rheumatoid arthritis (RA) treated? - What medicines are used to treat rheumatoid arthritis (RA)?
3. "The Different Doctors Caring for People Living with Rheumatoid Arthritis (RA)"	
 1. Learn the difference between a rheumatologist and a primary care provider. 2. Learn how important is to have a primary care provider in addition to a rheumatologist if you have rheumatoid arthritis (RA) 	
 A. Greetings between coaches and clients B. Verify that client has reviewed the RKOs and introduction to Session 3 C. Review of PALS assignments for Session 3 D. CARE RA Highlights of Session 3 E. Making a plan F. Plans for Session 4 G. PALS assignments for Session 4 H. Schedule Session 4 call 	
Required:
 
 - What is a rheumatologist? - What is a primary care provider (PCP)? - Do I need to see a primary care provider (PCP) if I already see a rheumatologist for my rheumatoid arthritis (RA)? - What can a primary care provider (PCP) do for me? - Which doctor should check my cholesterol levels if I have rheumatoid arthritis (RA)? 
Learn more:
 
 - What is a specialist or specialty doctor? - True or False: A primary care provider performs sick visit, injury, routine wellness care, and chronic disease management. A specialist focuses on treating specific conditions or organs.

4. "Requesting Cholesterol Test"	
 a. 1. To describe the importance of having a cholesterol test in order to learn what your risk is for heart attacks and strokes 2. To learn about how to communicate with your doctor about getting your cholesterol checked 3. To provide an overview of the medications used to lower your risk for heart attacks and strokes 	
 A. Greetings between coaches and clients B. Verify that client has reviewed the RKOs and introduction to Session 4 C. Review of PALS assignments for Session 4 D. CARE RA Highlights of Session 4 E. Making a plan: 
 A. Getting cholesterol test 
 - Rheumatologist? - Primary Care Physician? B. Doing something with the results 
 - Who will assess the CVD risk? - Who will manage cholesterol if CVD is high? C. Once you find out you have a test (feasibility): 
 - Make a plan for determining 10-year CVD risk - Make decision for initiation of statins F. Rehearse script to request a cholesterol test G. Plans for Session 5 H. PALS assignments for Session 5 I. Schedule Session 5 call 	
Required:
 
 - How can I talk with my doctor if they are in a rush? - What medications are used to treat high cholesterol? - Do statins lower my chances of blood pressure related problems like heart disease and stroke? - When do I have to start taking medicine to treat high cholesterol? - Can rheumatoid arthritis (RA) medications lower my risk for heart attacks and stroke? - Do I need to prepare for a cholesterol test? 
Learn more:
 
 - Can I take my rheumatoid arthritis (RA) medication with statins? - What are some common side effects of statins?
5. "How Did it Go?"	
 1. To discuss how the encounter with the rheumatologist or other physician on their care team was regarding having a cholesterol test done 2. To learn more about how exercise and diet can help people with RA lower their cholesterol. 3. To establish plans for follow up with a primary care physician for possible initiation of statins 	
 A. Greetings between coaches and clients B. Verify that client has reviewed the RKOs and introduction to Session 5 C. Review of PALS assignments for Session 5 D. CARE RA Highlights of Session 5 E. Discussion about the visit with the doctor F. Emphasize importance of following up with PCP G. Final questions and closure 
Note: Client should have completed the form with all the information for the 10-year pooled cohort risk equation.
	
Required:
 
 - What foods can help lower my cholesterol? - What is a healthy diet or eating pattern? - Can exercise help my rheumatoid arthritis (RA)? - Does exercise lower my risk for heart attacks and stroke if I have rheumatoid arthritis (RA)? - How can I exercise when I am in pain? - What should I expect when I receive the results of a cholesterol test? 
Learn more:
 
 - Can exercise make my rheumatoid arthritis (RA) symptoms worse? - What foods can help improve my rheumatoid arthritis (RA)? - What are the benefits of exercise?

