7.4 Post-intervention completion data collection point (All subjects in the study)

This call will take place around a week after completing the intervention by the blinded research assistant. This is a data collection call for all subjects in the study.

- **Surveys**
 - RAPID3
 - Social Support Survey
 - Patient Activation Measure (PAM)
 - Patient Health Questionnaire – 8 (PHQ- 8)
 - The General Self-Efficacy Scale (GSF)
 - Medication Understanding and Use Self-Efficacy Scale (MUSE)
- **Outcomes**
 - Cholesterol test
 - Initiating lipid lowering therapy
- **Program Evaluation**
 - Evaluation Survey
 - Focus Group/Interview

7.10 3-month post-intervention completion data collection point (All subjects in the study)

This call will take place around 3 months from completing the intervention by the blinded research assistant. This is a data collection call for all subjects in the study.

- **Complete patient generated health data (PGHD)**
 - RAPID3
 - Social Support Survey
 - Patient Activation Measure (PAM)
 - Patient Health Questionnaire – 8 (PHQ- 8)
 - The General Self-Efficacy Scale (GSF)
 - Medication Understanding and Use Self-Efficacy Scale (MUSE) Outcomes

- **Outcomes**

- Cholesterol test
- Initiating lipid lowering therapy

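### Section 7.2 and Table 2 schedule only programme evaluation for subjects who leave or are lost, so the primary outcome may not be asked of dropouts who can be reached

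*Combined protocol and SAP*

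**What the plan says.** Section 7.2 opens with a general rule: "All subjects will receive a baseline telephone call, the post-intervention follow up call, and the 3-month/final follow up call from the study team". The next sentence deals separately with subjects who are lost or who "drop out of the study before completion will be contacted to complete the program evaluation portions of the intervention".

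Table 2 (section 5.5) gives these people their own column, "Lost to Follow-Up/Dropouts". It has marks in two rows, the evaluation survey and the focus group/interview. The two rows under Outcomes (cholesterol test, start of lipid-lowering therapy) and all the survey rows are empty in that column.

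Sections 7.4 and 7.10 each describe their contact in the same way: "This is a data collection call for all subjects in the study". Section 7.2 adds that a blinded research assistant "will follow up by phone with those subjects that have not completed or partially completed the surveys to minimize missing data".

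Section 8.2 sets the analysis: "Analysis will be based on intention-to-treat, regardless of whether the subject completed the intervention program". It states a retention aim, "Every effort will be made to keep subjects in the study for the entire follow-up", and defines the endpoint: "The primary outcome is the percentage of patients with lipids checked (available now through national laboratory chain) or that reported having their lipids checked".

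**The concern.** The primary outcome is a yes/no fact that a subject can report in one answer. The plan already intends to contact people who have left, but the only content it lists for that contact is feedback on the programme. If staff follow the dropout column as printed, they can have a dropout on the telephone and end the call without learning whether a cholesterol test was done.

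An intention-to-treat analysis needs outcomes from everyone randomised, including those who leave. The sentence in 8.2 says how subjects are to be analysed once data exist. It does not say how the data are obtained from people no longer in the study. Outcomes that could have been had for one extra question would be missing, and the comparison would rest on a smaller and possibly selected group. The plan has its own interest here: the Maintenance part of Table 4 asks what effect attrition had on the conclusions about effectiveness.

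**Working it through.** **1. Which subjects are affected**

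- *Stops coaching, stays in the study.* Covered. Section 8.2 includes subjects whether or not they finish the programme, and the calls in 7.4 and 7.10 are for all subjects in the study.
- *Leaves the study or is lost.* The specific sentence in 7.2 and the dedicated Table 2 column both list programme evaluation only. Text and table agree, so the blank cells are unlikely to be a table-reading artefact.

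**2. Whether other text closes the gap**

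- The two check-in calls per subject (6.1 and 6.2) fall within the 5 weeks, before either outcome point.
- The telephone chase for incomplete surveys (7.2) and the retention aim (8.2) do not mention people who have left.
- Section 9 introduces the Table 4 questions as a tool for evaluating the programme with its participants, and the Effectiveness part includes cholesterol testing and statin initiation. However, Table 2 lists Outcomes and Program Evaluation as separate blocks, and the Effectiveness part refers to the statistical section for details. A mark against the evaluation survey therefore does not show that the outcome is asked.
- The laboratory source in 8.2 is not limited to completers, but nothing says it is used after a subject leaves.

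**3. Timing**

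Under 5.4 the intervention starts at least 6 weeks before the appointment. An evaluation contact made soon after an early dropout would come before the appointment and could not capture the outcome, even if the question were asked.

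**4. Illustrative size**

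Inputs from 8.1: p1 = 0.80 (CARE RA), p2 = 0.60 (control), one-sided alpha 0.05, 64 per arm. The mean proportion is 0.70. Section 5.3 plans 128 subjects = 2 × 64, so there is no allowance for missing outcomes.

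Reproducing the plan's figure (pooled variance, no continuity correction):

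n = [1.645·√(2·0.70·0.30) + 0.842·√(0.80·0.20 + 0.60·0.40)]² / 0.20² = [1.645·0.648 + 0.842·0.632]² / 0.04 = 63.9, rounded up to 64 per arm.

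Power = Φ{[0.20·√n − 1.645·0.648] / 0.632}. At n = 64 this is Φ{(1.600 − 1.066)/0.632} = Φ(0.844) = 80.1%.

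No dropout rate is stated. The nearest figure is the feasibility target in 3.2 that at least 80% complete the intervention, which is not a rate of missing outcomes. The losses below are assumptions, equal in both arms, with the rates among those observed unchanged:

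| Assumed loss | n per arm with outcome | One-sided power |
|---|---|---|
| 0% | 64 | 80.1% |
| 5% | 64 × 0.95 = 60.8 | 78.2% |
| 10% | 64 × 0.90 = 57.6 | 76.3% |
| 20% | 64 × 0.80 = 51.2 | 71.8% |

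These figures describe missing outcomes from any cause. They are not an estimate of what the Table 2 column alone would lose.

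**The case against.** The strongest reply is that the dropout column adds a contact and cancels nothing. Section 7.2 and the headings of 7.4 and 7.10 say all subjects. Outside the dropout column, Table 2 marks programme evaluation at one time point only, after the intervention. Someone who left earlier would miss it, which would explain an extra column that carries no date. On this reading the outcome calls continue on their usual dates. In addition, Table 4 places cholesterol testing under programme effectiveness and the evaluation survey itself is not shown. The laboratory source needs no contact and is not restricted to completers. What may be collected after withdrawal is normally a matter for the consent form, which was not available for this review.

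Much of this stands. The additive reading is reasonable, and the consent terms cannot be judged. A reader might infer that the plan stops outcome collection at dropout, or that it contradicts its own intention-to-treat promise. The documents do not support either inference: no sentence ends the calls or the laboratory look-up for people who leave.

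What does not stand is the claim that the point is settled. The only text written specifically for these subjects, in both section and table, omits the outcome, and the table keeps Outcomes apart from Program Evaluation.

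**Conclusion.** The point holds as a gap in the data-collection schedule for subjects who leave the study or are lost. The plan permits a reading under which a dropout is contacted and the primary outcome is not asked. That weakens the intention-to-treat analysis without invalidating it. Correcting it is a cheap improvement and needs no redesign.

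The size is illustrative. Under an assumed equal loss of 5% to 20% of outcomes, power falls by about 2 to 8 percentage points from 80.1%, on the plan's own one-sided basis. Only part of any such loss would come from this gap, and only part could be recovered.

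A reader might also infer that dropout would bias the comparison in a particular direction. The documents give no dropout rate for either arm, so no direction or amount of bias can be claimed.

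**What to change.** - **Table 2:** mark the cholesterol-test and lipid-lowering-therapy rows in the dropout column.
- **Section 7.2:** state that reachable dropouts who agree are asked whether they had a cholesterol test and whether they started lipid-lowering therapy, with dates. Ask at the post-appointment and 3-month points, or at the evaluation contact if that falls after the physician appointment.
- **Section 8.2:** state that the laboratory source is used for all randomised subjects in both arms, where consent allows.

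The cost is two questions and possibly one later call per consenting dropout, two marks in a table and a few sentences. No new staff or procedure is needed. Some subjects will stay unreachable, so the change reduces the gap but does not remove it.
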